10.1. Relivion Anticipated Adverse Events

Possible risks and adverse events that may be associated with the Relivion™ device are based on adverse events reports of similarity devices include, but are not limited to the following:

- Unpleasant sensation during treatment
- Scalp Numbness sensation during and after treatment
- Persistent tingling sensation after the treatment ends
- Pain
- Skin reaction (for example, irritation, lesion, burn) beneath the stimulation electrodes In this case, treatment should be temporarily discontinued.
- Redness of the skin under or around the electrodes. Skin redness usually disappears within several hours after treatment
- Sleepiness, fatigue or sleep disorders
- Sedative effect during or after treatment
- Dizziness during or after treatment
- Tension type headache after treatment

10.1.1. Reporting of Adverse Events

Please refer to **Table 2** for a list of the minimum AE reporting requirements for Investigators. If local regulations or IRB/EC require faster reporting, then the Investigator will adhere to those requirements. Reporting of all safety events to the Sponsor will be completed through Investigator submission of the AE eCRF in the remote data capture (RDC) system. In case of emergency only for SAEs (ex. RDC system is

 Neurolief Brain Innovation	THE RIME STUDY: ABRIDGED CLINICAL INVESTIGATION PLAN	Doc No.: CL-CIP-001 Abridged Ref Rev: REV.2 / 11JUN2019 Pg. 31 of 41
--	---	--

unavailable), the sponsor site representative may be contacted directly; this will not serve as a substitute for proper reporting on the appropriate eCRF.

Table 2: AE Reporting Requirements

Type	Report to	Reporting Timeframe (from time of learning of event)
Adverse Event (AE)	Sponsor	Within 10 working days
	IRB/EC	Per EC reporting requirements
Serious Adverse Event (SAE)	Sponsor	Within 24 hours
	IRB/EC	Per/IRB/ EC reporting requirements
Adverse Device Effect (ADE), Serious Adverse Device Effect (SADE) and Unanticipated Serious Adverse Device Effect (USADE/UADE)	Sponsor	Within 24 hours
	IRB/EC	Per EC reporting requirements
Device Deficiency	Sponsor	Within 48 hours
	IRB/EC	If SAE occurs due to the device deficiency, within 24 hours of learning of the event and per EC reporting requirements
	EC	Per EC reporting requirements

Events will be reviewed by the Sponsor to determine any reporting obligations to the FDA or Regulatory Authorities as well as IRB/EC. Reporting will occur within the timelines per local regulations and requirements. The Principle Investigator is responsible to report the events to the IRB/EC.

The sponsor shall immediately conduct an evaluation of any unanticipated events if determines that the events presents an unreasonable risk to subjects, report the results of such evaluation to the Regulatory authority and to reviewing IRB/EC and participating investigators within 10 working days after the sponsor first receives notice of the event.

10.1.2. Safety Monitoring and Adjudication of Adverse Events

The sponsor will review submitted AE information and may request supplemental information if needed. For SAE, U(SA)DE and ADE (as classified by the investigator) a narrative will be prepared and adjudicated for assessing the relatedness, seriousness and possible action items required. The sponsor may ask for further information or clarification from the investigator. A summary of the adjudication results will be

 Neurolief Brain Innovation	THE RIME STUDY: ABRIDGED CLINICAL INVESTIGATION PLAN	Doc No.: CL-CIP-001 Abridged Ref Rev: REV.2 / 11JUN2019 Pg. 32 of 41
--	---	--

issued; if different than investigator's report, PI will be notified and the information will be forwarded to Neurolief medical advisor for final adjudication.

Adjudicated events will serve as a basis for reporting AE/SAE. Differences between site-reported events and adjudicated events will also be presented and discussed in the report.

11. Statistical Considerations

11.1. Study Endpoint Variables

11.1.1. Primary endpoint variable

The primary endpoint, the proportion of subjects reporting reduction of migraine headache pain 2 hours post treatment initiation from severe or moderate to mild or no pain, or from mild to no pain, in their first treated migraine attack, when using active combined occipital and supraorbital transcutaneous nerve stimulation compared to sham stimulation, in subjects suffering from acute migraine headache, will be measured in the form of a binary variable which will be assigned the value of "1" if the subject reports such headache pain reduction without having used rescue medications, and "0" otherwise. Rescue medication use within the 2 hours post treatment initiation will result in the subject will be coded as "0" automatically.

11.1.2. Secondary endpoint variables

The three secondary endpoints will also be represented in the form of binary variables which will be assigned the value of "1" if the subject is a "responder" to each specific secondary endpoint, and "0" otherwise.

11.1.3. Exploratory endpoint variables

The exploratory endpoints will be measured in the form of a binary variables which will be assigned the value of "1" if the subject responds to each specific exploratory endpoint, and "0" otherwise.

Global Impression of Effect will also be measured via a 5-level Likert scale.

11.1.4. Safety endpoint variables

Incidence of all adverse events and complications by severity and relationship to study device.

11.2. Study Hypothesis

Study Hypothesis:

$$H_0: P_T = P_S$$

 Neurolief Brain Innovation	THE RIME STUDY: ABRIDGED CLINICAL INVESTIGATION PLAN	Doc No.: CL-CIP-001 Abridged Ref Rev: REV.2 / 11JUN2019 Pg. 33 of 41
--	---	--

$H_A: P_T \neq P_S$

Where PT and PS represent the proportions (%) of subjects reporting pain relief in the active treatment group and sham group respectively.

11.3. Sample Size Estimation

The sample size for this study was calculated to test the null hypothesis with a chi-squared test, even though the final analysis may employ a regression model and/or a Fisher's exact test.

The sample size is calculated to test the null hypothesis with 80% power at a 5% level of significance using the POWER procedure in SAS v9.4.

If we assume that 45% of the subjects in the active treatment arm will have successful pain relief versus 25% in the sham arm then 180 evaluable subjects are required, 90 per group. Allowing for a ~10% drop-out rate, a total of 200 (100 active vs. 100 sham) subjects should be enrolled in the study.

11.4. Interim Analysis

Planning one interim analysis that permits an increase in the sample size as described below does not additionally inflate the type I error [22-24]. In addition, the final analysis is performed using the conventional test as appropriate for the statistical hypothesis.

One interim analysis is planned once ~80% of the information is collected, i.e. the interim look will be performed after 144 evaluable subjects have been accrued. Based on the conditional power at the interim analysis, the study will either continue to the originally planned sample size if the result is "favorable", stop for futility if the result is "unfavorable", or we shall increase the sample size if the result is "promising". These decisions will be made based on the conditional power (CP), defined as the conditional probability that the final result will exceed a critical value at the interim given the observed effect size δ_1 = difference between pain reduction rates in the active versus control groups at the interim look. The following guidelines for sample size increase, depending on the zone into which CP falls at the interim, the calculated CPmin, the maximum sample size designated of 340 for the study and the % of the originally planned sample size at which the interim analysis will be performed. Following this principle does not inflate the Type I error.

The sponsor and the clinics will remain blinded throughout the study to the interim analysis results as well, only the decision made will be shared.

Notation:

n1= sample size at interim analysis

n2= sample size calculated based of effect size obtained at interim

 Neurolief Brain Innovation	THE RIME STUDY: ABRIDGED CLINICAL INVESTIGATION PLAN	Doc No.: CL-CIP-001 Abridged Ref Rev: REV.2 / 11JUN2019 Pg. 34 of 41
--	---	--

n_{max} = the highest sample size the company is willing to use/ can afford, $n_{max} = 340$ subjects and it is calculated based on a smaller effect size of 15% in the same manner as above in **Section 12.3**.

CP_{min} =is the calculated minimum CP based on the ratios n_{max}/n_2 , n_1/n_2 and the target study power (80%).

11.4.1. Procedure

After all the relevant data will be entered into the database, and the database cleaned, a soft lock to the database will be performed. An independent un-blinded statistician (not the study statistician) will perform the assessments described below. A designated data monitoring team will recommend whether to stop the study once the interim results are available.

At the interim analysis, the data of the evaluable subjects per ITT and mITT will be analyzed.

11.4.2. Blinding

Only the unblinded statistician and members of the interim decision team will be exposed to the interim report. The members of the data monitoring team may also have access to the unmasked information of the interim analysis. Investigators and company directors will only be informed of a decision to continue or to discontinue the trial, or to implement modifications in trial procedure. The un-blinded statistician who is responsible for conducting the interim analyses should ensure that the unmasked data is not available to any unauthorized person within or outside the company.

11.4.3. Decision Rules

The following are the decision rules for the interim analysis which will be performed upon accrual of 80% of the sample size, 144 evaluable subjects:

- If the result is “Unfavorable”, i.e. $CP < CP_{min} = 32.91\%$ (interim result is so disappointing that it is not worth increasing the sample size to retrieve conditional power) or if the difference between percentage of subjects reporting pain relief at the interim ($P_t - P_c$) is less than 0%, then stop the trial for futility.
- If the result is “Promising”, i.e. $32.91\% \leq CP < 80\%$ the sample size is increased recover the targeted power of 80%. The sample size used will be either the new calculated sample size based on the conditional power (as described in Sample size re calculation using conditional power Jonathan S. Denne Statist. Med. 2001; 20:2645–2660) or the predetermined maximum sample size of 340 subjects.
- If the result is “Favorable”, i.e. $CP \geq 80\%$ the interim results are sufficiently favorable and trial continues to the original sample size planned 180 without the need to adaptively increase the sample size.

Note that the interim analysis will be conducted on all population (ITT, mITT and PP analysis sets, see **Section 12.6**), and the study will be stopped due to futility only if the interim effects in both populations fall below the threshold.

11.4.4. Controlling the Alpha Level for the Primary Endpoint

The overall alpha level for this study is 5%. According to [references 1-2-3], planning an interim analysis that permits an increase in the sample size as described above does not inflate the type I error.

11.5. Randomization

Upon completion of the run-in period, eligible subjects will be randomly allocated (with a 1:1 ratio) to one of the following 2 treatment groups based on a randomization scheme using the permuted block method stratified by center:

- Group A – active (Relivion™) stimulation
- Group B = sham stimulation

The randomization scheme will be prepared by the study statistician using the SAS (version 9.4.) random number procedure. The block size will be random, and all study personnel will be therefore blinded to the randomization block size.

11.6. Analysis Populations

Intent-to-Treat (ITT) Population: The ITT population will include all randomized subjects, according to the ITT principle all subjects will be kept in a group as randomized.

Modified Intent-to-Treat (mITT) Population: The mITT population will include all randomized subjects who treat at least one eligible attack (excluding the "self-practice test"), with group assignment as treated.

Per-Protocol Population: The Per-Protocol population will include all subjects in the mITT population who completed the treatment period in compliance with the protocol and have no major protocol deviations, with group assignment as treated.

The ITT analysis set will serve as the main analysis set for all safety evaluations.

The efficacy analyses will be performed on the mITT analysis set.

The primary and secondary efficacy assessments will also be performed on the PP and the ITT analysis sets as a sensitivity analysis.

 Neurolief Brain Innovation	THE RIME STUDY: ABRIDGED CLINICAL INVESTIGATION PLAN	Doc No.: CL-CIP-001 Abridged Ref Rev: REV.2 / 11JUN2019 Pg. 36 of 41
--	---	--

11.7. Statistical Analysis

11.7.1. General Considerations

Statistical analyses will be performed using SAS® v9.4 (SAS Institute, Cary NC, USA). Statistical analyses and reporting will be performed in compliance with FDA Guidance E6 GCP, 21 CFR part 812, E9 and ISO 14155.

All statistical tests will be two-sided. The required significance level of findings will be equal to or lower than 5%, nominal p-values will be presented. Where confidence limits are appropriate, the confidence level will be 95%.

Continuous variables will be summarized by a mean, standard deviation, minimum, median and maximum and categorical variables by a count and percentage. For comparison of means (continuous variables), the two-sample t-test or the Wilcoxon rank sum test will be used as appropriate. For comparison of proportions (categorical variables), the chi-squared test or Fisher's exact test will be used as appropriate.

If multiple measurements are taken in a single patient, statistics described below will be appropriately modified to accommodate the within patient correlation.

Deviations from the planned analysis will be described, with proper justification, in the clinical study report.

11.7.2. Significance Level and Handling of Type I Error

Type I Error

The overall significance level for this study is 5% using two-tailed tests, except for treatment by site interaction that will be tested at a significance level of 10%.

Hierarchy Approach for Secondary Endpoint Analysis

The hierarchy approach will be adopted for the primary and secondary endpoints to control type I error due to multiple endpoint testing. Thus, the primary endpoint will first be tested and only if $p < 0.05$, will the secondary endpoints be tested. For the three secondary performance endpoints, the Benjamini–Hochberg step-up method will be used to adjust the p-values.

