On 02 July 2020 study enrollment was stopped, unfortunately, due to COVID-19; formal notice was sent out to the sites and ethical committees. Even though the company implemented all measures possible to ensure continued screening and randomization, subject retention and minimize loss to follow-up, but found that the completion of the originally planned randomized sample size was impossible .

Therefore, approximately 130 subjects for efficacy analysis were enrolled with 109 that have data for the primary endpoint, but that data remains blinded and has not yet been analyzed.

The approved study analysis plan utilizes a "sample size adaptive design" which calls for a single interim analysis for purposes of sample size adjustment, which was designed to occur when approximately 144 subjects had reached the primary endpoint. Due to the impact of the COVID-19 situation, the company would like to

modify the statistical plan while it remains blinded. The study has been stopped but the interim analysis has not been performed so that only one analysis - the final analysis - will be completed after data lock.

Based on the "Statistical Considerations for Clinical Trials During the COVID-19 Public Health Emergency" June 2020 FDA Guidance, and the fact that the Sponsor remains blinded to the treatment assignment and since no interim analysis was performed, no penalty to the alpha level is required. We shall address further analysis strategies in this revised SAP.

2 **EFFICACY ENDPOINTS**

2.1 **Primary Efficacy Endpoints**

The primary endpoint is the proportion (%) of patients reporting reduction in their pain level 2 hours post-treatment without rescue medications, from severe or moderate to mild or no pain, or from mild to no pain, in their first treated eligible migraine attack (excluding the "self-practice" treatment).

An eligible treatment is defined as a treatment meeting these basic criteria:

- no analgesics or other pain relief drugs or cannabis within 4 hours period before the treatment initiation; and
- no more than 30 minutes passed from the start of the migraine episode; and
- more than 48 pain free hours have passed since subject's previous Migraine episode; and
- subject did not wake up with a Migraine headache; and
- treatment with total stimulation time of at least 30 minutes of a "pass" session on the device log timeline, where pass is defined as a minimal stimulation of 2mA delivered).

2.2 **Secondary Efficacy Endpoints**

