Secondary efficacy endpoints include:

1. Proportion of subjects reporting improvement in their most bothersome migraine-associated symptom (MBS) other than a headache, 2 hours post-treatment initiation (if rescue therapy was not used), in their first eligible

treated migraine attack. MBS may be nausea, photophobia, phonophobia as defined by each subject prior to beginning of the treatment.

2. Proportion of subjects reporting reduction of migraine headache pain 1-hour post treatment initiation (if rescue therapy was not used), from severe or moderate to mild or no pain, or from mild to no pain, in their first eligible treated migraine attack.
3. Proportion of subjects who are pain free at 2 hours post treatment initiation (if rescue therapy was not used), in their first eligible treated migraine attack.

2.3

Additional efficacy endpoints

1. Proportion of subjects reporting freedom from their MBS other than a headache, 2 hours post-treatment initiation (if rescue therapy was not used), in their first eligible treated migraine attack.
2. Proportion of subjects who are pain free at 1-hour post treatment initiation (if rescue therapy was not used), in their first eligible treated migraine attack.
3. Proportion of subjects rating the subjects positive (score of 4 or 5) Global Impression of Effect of study device at the end of the study, defined as satisfied or very satisfied using a simple Likert-type scale whereas 1 = Very dissatisfied, 2 = dissatisfied, 3 = unsure, 4 = satisfied, 5 = Very satisfied.
4. Proportion of subjects reporting 2-24h headache relief, defined as headache relief at 2 hours without rescue medications, then no moderate to severe headache in the next 22 hours, and no use of rescue medication or additional stimulation.

Additional efficacy analyses that will be performed

1. Proportion of subjects reporting improvement in their MBS other than a headache AND reduction in their pain level, 1 and 2 hours post-treatment initiation (if rescue therapy was not used), in their first eligible treated migraine attack.
2. Proportion of subjects reporting freedom from their MBS other than a headache AND pain free, 1 and 2 hours post-treatment initiation (if rescue therapy was not used), in their first eligible treated migraine attack.
3. Rescue medicine usage.
4. Proportion of subjects who had pain relief in at least 50% of their eligible treated attacks at each timepoint.

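### Protocol 11.7.2 claims type I error control for the primary and secondary endpoints, but Benjamini-Hochberg on the three secondaries controls only the false discovery rate

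*Protocol*

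**What the plan says.** Protocol 11.7.2 makes three linked statements.

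- Level: "The overall significance level for this study is 5% using two-tailed tests" (the treatment-by-site interaction is the one exception).
- Purpose: "The hierarchy approach will be adopted for the primary and secondary endpoints to control type I error due to multiple endpoint testing".
- Mechanism: "the primary endpoint will first be tested and only if" its p-value is below 0.05 are the secondaries tested. Then, for the three secondaries, "the Benjamini–Hochberg step-up method will be used to adjust the p-values".

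No order among the secondaries and no further familywise step is given. The SAP takes precedence where it differs from the protocol. The supplied abridged SAP lists the same three secondaries in its section 2.2 and contains no multiplicity rule, so 11.7.2 is the only rule available. All three secondaries are read from the same subject's first eligible attack under the same no-rescue condition; the third, for example, is the proportion "pain free at 2 hours post treatment initiation (if rescue therapy was not used), in their first eligible treated migraine attack".

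**The concern.** Testing the primary first protects the primary: if it is null, a false claim of any kind requires a false primary rejection, and that is held at 5%. It does nothing to separate true from null secondaries once the primary has succeeded. From that point the only protection is Benjamini-Hochberg, which bounds the expected share of false rejections among all rejections. A truly effective secondary that is rejected dilutes that share and so relaxes the thresholds faced by the null ones.

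This is a pivotal study intended to support FDA clearance, and Protocol 11.7.1 says the analyses follow E9. An adjusted secondary p-value below 0.05 would be reported under wording that promises type I error control, when the method does not guarantee it.

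**Working it through.** **Inputs from the documents.** Two-sided level 5%, three secondaries, secondaries tested only if the primary has p < 0.05 (Protocol 11.7.2). Design rates of 45% and 25%, 90 per group (Protocol 11.3: "The sample size is calculated to test the null hypothesis with 80% power at a 5% level of significance"). The SAP Introduction gives "109 that have data for the primary endpoint".

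**Assumptions.** The documents give no correlation between the test statistics, so r runs from 0 to 0.9. Test statistics are taken as jointly normal with equal correlation.

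**The plan's own figure.** n per group = [1.960·√(2·0.35·0.65) + 0.842·√(0.45·0.55 + 0.25·0.75)]² / 0.20² = 88.1, so 89 against the stated 90. Power at 90 per group is 80.8%, and 180/0.9 = 200. The sample size reproduces. At 109/2 = 54.5 per group the power is 59.3%.

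**Ordered thresholds for three p-values, smallest first.**
- Benjamini-Hochberg, i × 0.05/3: 1.67%, 3.33%, 5%.
- Hochberg, 0.05/(4 − i): 1.67%, 2.5%, 5%.

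**Where Benjamini-Hochberg holds 5%.** With the primary certain to succeed and all three secondaries null, the error is 5.0% at r = 0, 4.7% at 0.5 and 3.7% at 0.9. With two strongly effective and one null, the single null faces the 5% threshold and the error is 5.0% at each r.

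**Where it does not.** Suppose one secondary is certain to be rejected and two are null. The true one takes the first rank. A false rejection then occurs if either null p-value is at or below the middle threshold, or both are at or below 5%. For independent tests:
- Benjamini-Hochberg: 1 − (1 − 0.0333)² + (0.05 − 0.0333)² = 0.0656 + 0.0003 = 6.58%.
- Hochberg: 1 − (1 − 0.025)² + (0.05 − 0.025)² = 0.0494 + 0.0006 = 5.00%.

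Bivariate normal integration of the same event gives:

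| r | 0 | 0.3 | 0.5 | 0.7 | 0.9 |
|---|---|---|---|---|---|
| Benjamini-Hochberg | 6.58% | 6.45% | 6.21% | 5.77% | 5.00% |
| Hochberg | 5.00% | 4.93% | 4.80% | 4.56% | 4.17% |

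Benjamini-Hochberg returns to 5% at r of about 0.90.

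**With realistic power for the primary.** The next figures are simulated (1 to 2 million draws per setting) for the primary plus three secondaries, one secondary effective and two null, with the secondaries tested only after a significant primary. Mean z is 1.96 + 0.84 = 2.80 for 80% power and 1.96 + 1.28 = 3.24 for 90%. For 109 subjects it is 0.20/√(0.435/54.5) = 2.24. The effective secondary has the same mean z as the primary.

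| Benjamini-Hochberg error | r = 0 | 0.3 | 0.5 | 0.7 |
|---|---|---|---|---|
| 80% power | 4.6% | 4.3% | 3.8% | 3.1% |
| 90% power | 5.5% | 5.1% | 4.4% | 3.5% |
| 109 subjects | 3.1% | – | 3.1% | – |

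At 80% power, the part of the error that favours active, which is the part that could become a benefit claim, is 2.4%, 2.9%, 3.1% and 2.9% across r. Under Hochberg it is 1.9%, 2.3%, 2.4% and 2.3%. Half of a two-sided 5% is 2.5%.

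**The case against.** The strongest reply is that the plan's own assumptions barely reach the excess. At 80% power for the primary and the true secondary, the error is below 5% throughout. If the true secondary is made overwhelming while the primary stays at 80% power, the error is 5.3% at r = 0 (0.80 × 6.58%), 4.8% at 0.3 and 4.1% at 0.5. With 109 subjects and an overwhelming secondary it is 4.0%, 3.8% and 3.4%. A larger breach needs a primary effect stronger than the one planned. This stands, and it limits the practical size.

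Four further points have some force.

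- **Discrete tests.** Protocol 11.7.5 names both chi-squared and Fisher's exact tests for the secondaries and does not say which p-value is adjusted. With 55 against 54 subjects, independent nulls, an overwhelming true secondary, a certain primary and assumed null rates of 10% to 50%, exact calculation gives 4.5% to 5.4% for Fisher and 6.2% to 6.9% for chi-squared. Fisher would remove most of the excess, but the plan does not commit to it.
- **Abridged SAP.** The full SAP may contain another rule. If so, pointing to it closes the matter.
- **Reading of the text.** Section 11.7.2 never uses the word familywise, and its type I error sentence could be read as describing only the primary-first step. But the sentence names both primary and secondary endpoints and gives multiple endpoints as the reason.
- **The worst case is conditional.** The 6.58% rests on joint normality. Under arbitrary dependence the bound is 8.33% with two nulls (2 × 3.33% + 1.67%) and 9.17% with three (5% × (1 + 1/2 + 1/3)). Dependence that extreme is implausible for outcomes of the same attack.

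These points bear on the size of the excess or on whether the rule still applies. None of them gives Benjamini-Hochberg the property that 11.7.2 claims.

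**Conclusion.** The concern holds. On the supplied text, 11.7.2 attributes to the secondary analysis a property that its method lacks. The primary endpoint and the study's success criterion are untouched. The maximum excess is about 1.6 points (6.58% − 5%). It requires an almost certain primary, exactly one overwhelming secondary, two nulls, uncorrelated nulls and jointly normal statistics. It shrinks with the positive correlation to be expected from outcomes of one attack, and at design power the two-sided error is below 5%. The correction is worth making because the claim is wrong as written and cheap to correct while the data are blinded, not because large inflation is likely.

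**What to change.** Amend one sentence in Protocol 11.7.2 and put the same rule in the SAP, before unblinding. The SAP states that the data are still blinded and that no interim analysis was done, so the change would be clean at that point. Either option works.

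1. **Hochberg step-up at 5%** for the three secondaries, tested only if the primary has p < 0.05. Only the middle threshold changes, from 3.33% to 2.5%. At 80% design power and r = 0.5, power per true secondary (primary also significant) falls from 63.5% to 61.3% if two are effective, and from 66.7% to 65.9% if all three are. Hochberg itself needs a dependence condition. It held 5% at every correlation examined here; Holm or a fixed sequence would hold 5% without that condition.
2. **Keep Benjamini-Hochberg**, state that only the false discovery rate is controlled for the secondaries, and confine the type I error claim to the primary. This costs no power but gives up the familywise claim for the secondaries.

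Under either option, state whether the chi-squared or the Fisher p-value enters the adjustment.
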